### **3.3 Estimated Time for Completion of Study Enrollment**

Approximately two years.

## **4 SUBJECT PARTICIPATION, DISCONTINUATION, AND WITHDRAWAL**

MCW must follow all MCW IRB requirements and policies regarding subject participation, found here:

<https://www.mcw.edu/HRPP/Policies-Procedures.htm>

### **4.1 Subject Status**

Subject statuses throughout the trial are defined as follows:

- Prescreening: pre-consent (subject considering trial or study staff considering patient for the trial per institutional recruitment methods).
- Screening: period after consent, but prior to eligibility confirmation.
- Consented: consented, prior to eligibility confirmation.
- Eligible: the local investigator confirms all eligibly criteria apply.
- On study/enrolled: date eligibility is confirmed.
- On arm: date of enrollment.
- On treatment: first day treatment was given to the last day treatment was given.
- Off treatment: the last day treatment was given.
- On follow-up: from last day of treatment to the end of follow-up period.
- Off study: follow-up period completed, with no additional data gathered.
- Withdrawn: subject fully withdraws consent (i.e., refuses ALL follow-up, even survival) or is taken off study by the local principal investigator.

### **4.2 Prescreening and Screening Log**

The MCW study principal investigator regularly reviews screen failure reasons to understand barriers to accrual and consider amending eligibility criteria. Screen failures are defined as participants who were considered for the trial to participate in the clinical trial with or without consent but are not subsequently assigned to the study intervention or enrolled in the study. MCWCC CTO will follow its SOPs regarding prescreening and screening tracking.

### **4.3 Consent**

Investigators or their appropriate designees will identify potentially eligible subjects from their clinics, subject self-referrals, referrals from other clinicians, and/or other IRB-approved recruitment methods. No study conduct, including subject prescreening, can occur until after IRB approval.

A written, signed informed consent form (ICF) and a Health Insurance Portability and Accountability Act (HIPAA) authorization must be obtained before any study-specific

assessments are initiated. A signed ICF copy will be given to the subject and a copy will be filed in the medical record (per local IRB policies and SOPs). The original will be kept on file with the study records.

#### **4.4 Screening Procedures**

Refer to the study calendar of events.

Visit procedures that were performed as standard of care prior to consent (without the specific intent to make the subject eligible for the trial), may count toward screening tests and eligibility if they are within the screening window.

#### 4.5 Eligibility Confirmation

Study staff must adhere to MCWCC CTO SOPs regarding eligibility review/confirmation.

No waivers of protocol eligibility will be granted. When clinical factors relating to an eligibility item are unclear or questionable, the study PI ([[name], [contact]](mailto:[contact])) can only provide guidance or clarification on eligibility.

#### Inclusion Criteria

1. Voluntary written consent must be given before performance of any study-related procedure that is not part of standard medical care, with the understanding that consent may be withdrawn by the subject at any time without prejudice to future medical care.
2. English speaking.
3. Female or male subject's  $\geq$  18 years old at the time of informed consent.
4. Radiographically confirmed solid tumor brain metastases.
5. Criteria for surgical resection of at least one metastasis per neurosurgeon discretion.
6. Stereotactic radiosurgery candidate per radiation oncologist discretion.
7. A diagnostic MRI brain or CT head demonstrating the presence of one to four solid tumor brain metastases and lesion to be resected no more than 5 cm in any direction, performed within 30 days prior to stereotactic radiosurgery.
8. For known and unknown primary, ds-GPA estimated median survival no less than six months.
9. Surgical resection able to be performed within one to 10 days after radiosurgery.
10. Patients currently on cytotoxic chemotherapy or immunotherapy are eligible, not including anti-VEGF therapy.
11. Female subjects who:
  - a. Are postmenopausal for at least one year before the screening visit, OR
  - b. Are surgically sterile, OR

If they are of childbearing potential:

- i. Agree to practice one highly effective method and one additional effective (barrier) method of contraception, at the same time, from the time of signing the informed consent through four months after the last study Intervention (female and male condoms should not be used together), OR
- ii. Agree to practice true abstinence, when this is in line with the preferred and usual lifestyle of the subject. (Periodic abstinence [e.g., calendar, ovulation, symptothermal, post-ovulation methods] withdrawal, spermicides only, and lactational amenorrhea are not acceptable methods of contraception.)

CRC Initials: \_\_\_\_\_

Date: \_\_\_\_\_

Investigator/Enrolling Physician Initials: \_\_\_\_\_

Date: \_\_\_\_\_

12. Male subjects, even if surgically sterilized (i.e., status post-vasectomy), who:

- Agree to practice effective barrier contraception during the entire study treatment period from the time of signing the informed consent through and through four months after the last study intervention (female and male condoms should not be used together), OR
- Agree to practice true abstinence, when this is in line with the preferred and usual lifestyle of the subject. (Periodic abstinence [e.g., calendar, ovulation, symptothermal, postovulation methods for the female partner] withdrawal, spermicides only, and lactational amenorrhea are not acceptable methods of contraception.)

### **Exclusion Criteria**

- Patients who received anti-VEGF therapy within six weeks prior to enrollment, as there is increased risk of fatal brain hemorrhage with surgical resection.
- Non-English speaking.
- Major medical illnesses or psychiatric impairments, which in the investigator's opinion will prevent administration or completion of the protocol therapy and/or interfere with surveillance.
- Patients with more than four brain metastases on MRI brain.
- Lesion to be resected is more than 5 cm in any dimension.
- Patients with leptomeningeal metastases documented by MRI or CSF evaluation.
- Previous whole-brain radiation therapy.
- Previous radiation therapy to the lesion to be resected.
- Planned adjuvant focal therapy including additional radiation therapy to the brain.
- Not a surgical candidate per neurosurgeon discretion.
- Not a stereotactic radiosurgery candidate per radiation oncologist discretion.
- Surgery unable to be performed between one to 10 days after radiosurgery.
- Women who are pregnant or nursing as treatment involves unforeseeable risks to the fetus or child.
- Patients who have a known or unknown primary and have an estimated median survival of less than six months per ds-GPA.

*"I have reviewed all inclusion and exclusion criteria and confirm the subject is eligible."*

---

(CRC Signature)

---

(Date)

---

(Investigator/Enrolling Physician Signature)

---

(Date)

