## STUDY SCHEMA

## STUDY CALENDAR

Procedure	Screening 	Radiosurgery Delivery	Surgical Resection	Post-Surgical Resection Visit	Follow-up  (until 18-months from post-surgical resection visit) (18 months)
Study Day/Visit Day	Day – 30 to Enrollment	Day 1	Day 2 (+8 days)	1-month ±7 days from radiosurgery	Every 3 months ±14 days
Informed Consent	X				
AE Reporting	X	X	X	X	
Concomitant Medications	X	X	X	X	X
SRS		X		X	
Physical Exam 	X			X	X
Medical History	X				
ECOG Performance Status	X			X	X
Pregnancy Test (Serum or Urine) 	X				
Neurocognitive Testing 	X				
QOL Questionnaire 	X			X	X
MRI (Brain) 	X			X	X

1. All screening procedures must occur within 30 days prior to enrollment. Treatment must start within 14 days of enrollment.
2. If a subject has disease progression/relapse or subject withdrawal, then they will be followed as per follow-up requirements.
3. Including height and weight on screening. Temperature, HR, RR, BP and O2 sats or as per institutional standards at all timepoints.
4. For women of childbearing potential, a negative pregnancy test (serum or urine) must be obtained within 30 days prior to the first study intervention.
5. Neurocognitive testing: Multilingual Aphasia Examination Controlled Oral Word Associated Test (COWAT), Trail Making Test, Parts A and B (TMT), and Hopkins Verbal Learning Test-Revised (HVLT-R).
6. QOL Questionnaire: MDASI-BT, EQ-5D-5L.
7. MRI (brain) w/ contrast. Radiographic assessments will be completed as per RANO criteria (see Appendix 3).

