## **2.3 Primary Endpoint**

1. Feasibility for this study will be defined as 50% of enrolled study subjects undergoing the surgical resection as per the protocol.
2. Measure rate of local control at the resection cavity any new tumors by post-treatment MRI.

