## **3.2 Design of the Current Study**

Enrolled patients will receive GK-SRS to all metastases followed by surgical resection of resectable metastases within one to 10 days following GK-SRS. Pathologic specimens will be analyzed, and the patient will enter a standard pattern of surveillance (brain MRI every three months for two years).

Quality of life will be assessed every three months, and neurocognitive evaluations will be performed every six months. These parameters will be compared to baseline testing performed at the time of enrollment. Local control, CNS progression-free survival, overall survival, rates of leptomeningeal carcinomatosis, rates of radiation necrosis, and steroid requirements will also be documented and compared with historically reported rates.

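### Feasibility is measured only among patients already judged able to have resection in the window, and the missing-data rule in section 7.3 contradicts its enrolled denominator

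*Combined protocol and SAP*

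**What the plan says.** Section 2.3 defines the first primary endpoint: "Feasibility for this study will be defined as 50% of enrolled study subjects undergoing the surgical resection as per the protocol". Section 3.2 describes the protocol sequence as radiosurgery to all metastases, then "surgical resection of resectable metastases within one to 10 days following GK-SRS".

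Section 4.5 uses the same event and window twice as an entry condition. Inclusion criterion 9 reads "Surgical resection able to be performed within one to 10 days after radiosurgery", and the exclusion list contains "Surgery unable to be performed between one to 10 days after radiosurgery". Surgical candidacy (inclusion 5 and its own exclusion) and serious illness that would prevent protocol therapy are covered by separate criteria.

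Section 4.1 fixes when a subject joins the denominator: "On study/enrolled: date eligibility is confirmed". The Study Calendar puts treatment after that: "Treatment must start within 14 days of enrollment".

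Section 4.2 describes screen failures as people considered for the trial "but are not subsequently assigned to the study intervention or enrolled in the study", and says that the principal investigator "regularly reviews screen failure reasons to understand barriers to accrual". The endpoint makes no use of that log.

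Section 7.3 says that subjects who do not finish follow-up are treated as attrition and left out of the primary and secondary objectives, apart from possible demographic description. Sections 7.1 and 7.2 name feasibility as the primary objective but give it no analysis. The only calculation is for local control.

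**The concern.** What the endpoint counts is also what the entry criterion requires to be achievable. A feasibility study of a two-step sequence should show how often both steps can be delivered on schedule. Here, patients for whom the schedule is foreseen to fail are removed before counting starts. Because candidacy and fitness have their own criteria, what the window criterion adds is mainly scheduling, and deliverability on schedule is a large part of what such a study is meant to learn.

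At stake is how a result at or above 50% is read. It would support a statement about patients with a workable surgical plan. It would not, without further data, support a statement about otherwise eligible patients in general. The conflict with section 7.3 adds a second problem: even among enrolled subjects, the plan does not settle who is counted.

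**Working it through.** **No feasibility figure to reproduce.** The plan gives no calculation behind the 50% threshold. The precision statement in 7.1 concerns local control and does not bear on this point. I read the threshold as at least 50%.

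**Step 1: order of events.** Eligibility confirmed (inclusion 9 and the exclusion applied), then enrolled (4.1), then radiosurgery within 14 days (Study Calendar), then resection in the window (3.2). Two consequences follow.
- A patient forecast before enrolment to miss the window is a screen failure and lies outside the denominator.
- A subject whose surgery falls through after enrolment is already in the denominator and counts as a failure.

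**Step 2: enrolled rate against candidate rate.** Let r be the share of enrolled subjects resected per protocol, s the share of otherwise eligible candidates excluded on the window criterion alone, and w the share of those excluded who would in fact have been resected in the window. Then

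candidate rate = (1 − s) × r + s × w.

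This is below r whenever s > 0 and w < r. The documents give none of the three, so all values here are assumptions. Taking w = 0 (every adverse forecast correct), the candidate rate reaches 50% at s = 1 − 0.5/r:

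| r (assumed) | s at which the candidate rate is 50% |
|---|---|
| 0.80 | 1 − 0.5/0.80 = 37.5% |
| 0.90 | 1 − 0.5/0.90 = 44.4% |
| 1.00 | 1 − 0.5/1.00 = 50.0% |

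If w > 0, more screening-out is needed.

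**Step 3: effect on meeting the threshold.** Let π be the share of candidates in whom the sequence can be delivered, and f the share of would-be failures that the criterion removes. The rate among enrolled is q = π / [π + (1 − π)(1 − f)]. With π = 0.40 assumed:

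| f (assumed) | q | Chance of at least 5 of 10 | Chance of at least 8 of 15 |
|---|---|---|---|
| 0 | 0.40 | 0.37 | 0.21 |
| 0.25 | 0.40/0.85 = 0.47 | 0.55 | 0.41 |
| 0.50 | 0.40/0.70 = 0.57 | 0.78 | 0.71 |
| 0.75 | 0.40/0.55 = 0.73 | 0.97 | 0.97 |

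A sequence deliverable in 40% of candidates could thus be likely to pass, if the criterion removes half or more of the failures. This shows direction and sensitivity; it does not estimate what will happen.

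**Step 4: section 7.3 against section 2.3.** Section 2.3 counts all enrolled subjects. Section 7.3 removes non-completers from the primary objectives, and itself describes those objectives as concerning feasibility. With the maximum enrolment of 15 and 7 resected (assumed), the endpoint reads 7/15 = 46.7%. If one unresected subject does not complete follow-up and is dropped, it reads 7/14 = 50.0%; with two dropped, 7/13 = 53.8%. The rule can also work the other way: from 8/15 = 53.3%, dropping two resected non-completers gives 6/13 = 46.2%. The direction is not fixed, but one or two subjects can decide the result.

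**Step 5: the window itself.** The Study Calendar places radiosurgery on Day 1 and resection on Day 2 with an allowance of 8 further days, so the latest is Day 10, nine days after radiosurgery. Sections 3.2 and 4.5 allow up to 10 days. These places must be reconciled, because they decide which resections count as per protocol.

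**The case against.** The strongest defence is that the endpoint openly refers to enrolled subjects. Requiring that both parts of a sequence be possible before giving the first is an ordinary entry condition. For the question of how many patients planned for surgery in the window actually get it, the rate is not biased, provided that everyone enrolled is counted. Deterioration, withdrawal or a lost theatre slot after enrolment still counts against feasibility. Section 4.2 already requires review of screen-failure reasons. All of this stands. It limits the overstatement to the wider candidate population and means that the criterion itself need not go.

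The magnitude also rests on assumed inputs. Nothing in the documents suggests that 38% to 50% of otherwise eligible patients would be excluded on this criterion, or that scheduling is the main way in which the sequence would fail.

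A reader might infer something stronger from the exclusion's wording, which refers to surgery after radiosurgery: that an irradiated patient who misses the window meets the exclusion and could be declared ineligible afterwards. The documents do not support that. Eligibility is confirmed before treatment (4.1, Study Calendar) and attested by dated signature at the end of 4.5. Screen failures are people not enrolled or not assigned to the intervention (4.2). Stopping treatment does not end participation, and treated subjects who stop are not replaced (4.6). No section provides for reclassification. None expressly forbids it either, which justifies a clarification of wording and no more.

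**Conclusion.** The point holds in a limited form. The overlap between entry criterion and endpoint is literal, and nothing in section 7 adjusts for it. The reported rate will describe delivery among patients already forecast to be deliverable. It will overstate feasibility among otherwise eligible candidates if anyone is excluded on this criterion alone and those excluded would have been resected less often than those enrolled. The size cannot be obtained from the documents; the 44% figure assumes r = 0.90 and w = 0.

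The conflict between 2.3 and 7.3 depends on no assumed rate. As written, the two sections give different denominators, and at 15 subjects or fewer the difference can change whether the threshold is met.

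This concerns the first primary endpoint and is cheap to correct, so it should be corrected. It does not invalidate the design, and I would not rank it among the changes that the trial cannot do without.

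**What to change.** Leave the surgical window as a criterion and make three changes.

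1. In 2.3 and 7.3, state that every enrolled subject stays in the feasibility denominator, that a resection missed or not done per protocol for any reason counts as a failure, and that feasibility is exempt from the exclusion of non-completers in 7.3.
2. From the screening log under 4.2, tabulate patients excluded solely on the surgical-window criterion. Report feasibility twice: resected / enrolled, and resected / (enrolled + window-only exclusions). The log must record when this was the only reason. The second rate treats all those patients as not deliverable, so it should be presented as a conservative companion figure.
3. As a minor clarification, word inclusion 9 and the matching exclusion as judged once, at eligibility confirmation.

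The cost is a few sentences in 2.3, 4.5 and 7.3 and one table from a log already kept. The feasibility figure may look less favourable. No procedure, visit or sample size changes.

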## **4.6 Discontinuation of Study Treatment, Withdrawal, and Compliance**

Discontinuation from the study treatment does not mean discontinuation from the study. Subject will be considered in follow-up; study procedures should still be completed as indicated by the study protocol and AEs/SAEs will continue to be reported according to this protocol.

In the absence of treatment delays due to adverse events, study treatment/intervention may continue until:

- Disease progression.
- General or specific changes in the subject's condition renders the subject unacceptable for further treatment in the investigator's judgment.
- Intercurrent illness that prevents further treatment administration.
- Subject decides to withdraw from the study.
- The subject has significant noncompliance with the protocol (see below).
- Unacceptable adverse event(s) and/or dose level reduction beyond requirements as detailed in this protocol.
- Study stopping rules are met.

Subjects who sign the informed consent form, and are enrolled and receive the study intervention, but subsequently withdraw, or are withdrawn or discontinued from the study will not be replaced.

### **Consent Withdrawal**

A subject may decide to withdraw from the study at any time. MCWCC CTO will follow its IRB of record's SOPs regarding consent withdrawal.

If a subject intends on withdrawing consent, staff should confirm which of the following options the subject chooses and document the discussion:

- Full consent withdrawal with no study follow-up.
- Selective consent withdrawal from interventional portion of the study but agree to continued follow-up of associated clinical outcome information.

### **Investigator-initiated Withdrawal**

The investigator will withdraw a subject whenever continued participation is no longer in the subject's best interests. Reasons for withdrawing a subject include, but are not limited to, disease progression, the occurrence of an adverse event or a concurrent illness, a subject's request to end participation, a subject's noncompliance or simply significant uncertainty on the part of the investigator that continued participation is prudent. The reason for study withdrawal and the date the subject was removed from the study must be documented.

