## 1.6 Leptomeningeal Carcinomatosis

With increased utilization of postoperative SRS in place of WBRT and expanding data on outcomes, specific patterns of CNS failure are becoming clearer. A number of studies report excellent local control rates with postoperative SRS (up to 83 to 94% at 24 months) but with distant intracranial failure rates of 40 to 60% within 12 months. This is consistent with previously published data demonstrating inferior distant brain control with SRS compared to SRS with adjuvant WBRT.

Of increasing interest is the incidence of leptomeningeal carcinomatosis in patients with solid tumors and brain metastases. Rates of leptomeningeal disease with solid tumors are reported to be in the range of 5 to 15%. Risk factors for leptomeningeal involvement include breast cancer histology (particularly triple-negative receptor status and infiltrating lobular carcinoma), as well as non-small cell lung cancer and melanoma histologies. Treatment options at the time of leptomeningeal failure typically include radiation, intrathecal chemotherapy, and/or systemic chemotherapy depending on histology. Prognosis with leptomeningeal metastasis is poor, with reported survival in the range of two to six months.

Neurosurgical risk factors for leptomeningeal carcinomatosis include piecemeal resection, opening of the ventricular system, and infratentorial lesions. In the setting of up-front surgery, the hypothesis is that any anatomic disruption that allows cerebrospinal fluid (CSF) contamination with tumor cells may predispose for leptomeningeal spread. Although postoperative SRS

provides excellent local control at the resection cavity, it does not address tumor cells that have seeded the CSF. Currently reported rates of leptomeningeal failure after surgery with postoperative SRS for brain metastases are in the range of 8 to 24%.

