## **2.4 Secondary Endpoint(s)**

1. CNS progression-free survival and overall survival will be evaluated at six, 12, and 18 months following surgical resection.
2. Rates of leptomeningeal carcinomatosis using preoperative GK-SRS will be documented and compared to historically cited rates for postoperative GK-SRS.
3. Incidence of radiation necrosis will be measured by post-treatment MRI.
4. Quality of life measures will be collected and will be compared to historically cited data.

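### Section 4.6 allows removal from the study for disease progression while calendar footnote 2 keeps progressors in follow-up; nothing says which governs, so post-progression outcomes can be lost

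*Combined protocol and SAP*

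**What the plan says.** The Investigator-initiated Withdrawal part of section 4.6 sets the test: "The investigator will withdraw a subject whenever continued participation is no longer in the subject's best interests". It then gives examples: "Reasons for withdrawing a subject include, but are not limited to, disease progression, the occurrence of an adverse event or a concurrent illness". It treats this as leaving the study, not only stopping treatment: "The reason for study withdrawal and the date the subject was removed from the study must be documented".

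Section 4.1 defines the resulting status: "Withdrawn: subject fully withdraws consent (i.e., refuses ALL follow-up, even survival) or is taken off study by the local principal investigator".

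Footnote 2 of the Study Calendar points the other way: "If a subject has disease progression/relapse or subject withdrawal, then they will be followed as per follow-up requirements".

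Section 4.6 opens by saying that a subject who stops study treatment remains on study and in follow-up. It lists progression there as one of the events that end treatment.

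On endpoints, section 2.4 states: "CNS progression-free survival and overall survival will be evaluated at six, 12, and 18 months following surgical resection". It also calls for leptomeningeal rates set against historical rates and for radiation necrosis on post-treatment MRI. Section 2.3 makes local control at the resection cavity a primary endpoint.

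**The concern.** The intervention is radiosurgery followed by resection one to 10 days later. Progression found on a later surveillance MRI comes when there is no study treatment left to stop. Withdrawing the subject at that point can end only observation.

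Overall survival, leptomeningeal disease, necrosis and later cavity recurrence all have to be observed beyond a first progression. Section 1.6 cites "distant intracranial failure rates of 40 to 60% within 12 months" after postoperative radiosurgery, so a first brain failure may well be common. If progressors are also more likely to die or to develop leptomeningeal spread, losing them is informative. The remaining data would look better than the truth, and section 3.2 sets those data against historical rates.

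This is separate from the section 7.3 rule on subjects who do not complete follow-up. That rule decides how incomplete data are analysed; the point here is whether the data are collected. Correcting 7.3 alone would not recover deaths that nobody recorded.

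**Working it through.** **Can the texts be read together?**

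| Place | Event | Consequence |
|---|---|---|
| 4.6, opening | Treatment stopped, progression included | Stays on study, in follow-up |
| 4.6, investigator-initiated withdrawal | Progression as an example reason, under a best-interests test | Removed from the study, date recorded |
| 4.1, Withdrawn | Taken off study by the investigator | Same status as refusing all follow-up, survival included |
| Calendar footnote 2 | Progression, relapse or withdrawal | Followed |

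The opening of 4.6 covers only stopping treatment, so it does not answer the withdrawal paragraph. Footnote 2 covers withdrawal too, but conflicts with the 4.1 definition. The Consent Withdrawal part of 4.6 offers a selective option that keeps follow-up; investigator-initiated withdrawal offers none. No order of precedence is given, so staff could comply with either text. Progression in 4.6 is not limited to the brain, so extracranial progression could also end follow-up.

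**How large could the effect be?** The plan gives no figure to reproduce, so this is an illustration.

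Inputs:
- From the documents: progression p = 0.40 to 0.60 by 12 months (section 1.6, postoperative radiosurgery), assumed to apply here. In 10 completed subjects that is 4 to 6.
- Assumed: death hazard d0 = 0.01 or 0.02 per month before progression and d1 = 0.05 or 0.08 after, all constant. Withdrawal happens at progression, is unrelated to later risk among progressors, and is handled as Kaplan-Meier censoring.

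Formulas, t in months:
- Progression hazard λ = −ln(1 − p)/12, which is 0.0426 for p = 0.40 and 0.0764 for p = 0.60.
- Progression-free and alive: P0(t) = exp(−(λ + d0)t).
- Progressed and alive: P1(t) = λ[exp(−d1·t) − exp(−(λ + d0)t)]/(λ + d0 − d1).
- True OS(t) = P0(t) + P1(t).
- All progressors withdrawn: estimated OS(t) = exp(−d0·t).
- Fraction w withdrawn: the observed hazard is [d0·P0 + d1(1 − w)P1]/[P0 + (1 − w)P1]. Estimated OS is exp of minus its integral from 0 to t.

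One case in full (p = 0.60, d0 = 0.01, d1 = 0.08, t = 12): P0 = 0.3548. P1 = 0.07636 × (0.38289 − 0.35477)/(0.08636 − 0.08) = 0.338. True OS = 0.693. Estimate with all progressors withdrawn = exp(−0.12) = 0.887. Gap = 0.194.

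Ranges over all eight combinations of p, d0 and d1:

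| | 12 months | 18 months |
|---|---|---|
| True OS | 63 to 81% | 46 to 69% |
| Estimate, all progressors withdrawn | 79 to 89% | 70 to 84% |
| Overstatement, all withdrawn | 5.4 to 19.4 points | 9.5 to 31.6 points |
| Overstatement, half withdrawn | 2.3 to 7.0 points | 3.6 to 9.5 points |

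The gaps are taken within each combination, not between the ends of the ranges.

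**The case against.** The strongest reply is that the plan does not take subjects off study at progression. Withdrawal turns on the subject's best interests, progression is only one example reason, and follow-up is described as standard surveillance, which progression does not obviously make harmful. Footnote 2 is specific and on point, while the withdrawal paragraph reads as generic wording. This stands in part. A reader might infer that follow-up must stop at the first brain failure. The documents do not support that: loss of follow-up is permitted, not required. But footnote 2 is not given precedence, and it conflicts with section 4.1.

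A reader might also infer that withdrawal can never affect treatment. That goes too far, because between radiosurgery and surgery a withdrawal can still stop the resection. The point is confined to progression after surgery.

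A third reply is that this is a pilot with 10 completed subjects. Feasibility is settled at surgery, CNS progression is itself an event for CNS progression-free survival, and the exposed outcomes are mostly secondary, with no test against historical rates specified in section 7.2. That stands and lowers the priority. It does not remove the problem, since the plan still intends those comparisons and later cavity recurrence bears on a primary endpoint.

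Finally, the hazards have no source in the documents, and section 7.3 as written would drop subjects with incomplete follow-up instead of censoring them. Both are true, so the figures are illustrative and describe an analysis that censors.

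**Conclusion.** The contradiction is real and unresolved. Applied as written, sections 4.6 and 4.1 allow observation to end at progression, and the data lost would come from subjects plausibly at highest risk.

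The direction of the survival bias needs only a higher death risk after progression than before. Its size depends on the assumed hazards and on how many progressors are withdrawn. The gaps of about 5 to 19 points at 12 months and 9.5 to 32 at 18 months are the extreme in which all are withdrawn; a reader should not take them as the expected bias. With half withdrawn the overstatement is about 2 to 7 and 3.6 to 9.5 points.

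The exposed outcomes are overall survival, leptomeningeal disease, necrosis and any cavity recurrence that follows an earlier progression. This should be fixed, but it does not undermine the feasibility aim.

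**What to change.** Reconcile Study Calendar footnote 2 with sections 4.1 and 4.6:

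- In 4.6, make clear that disease progression is not in itself a reason to end observation, and keep ending study treatment distinct from ending follow-up.
- State that footnote 2 governs: every subject who received radiosurgery stays in follow-up for cavity status, leptomeningeal disease, necrosis and survival to the end of the follow-up period, unless consent for follow-up is withdrawn.
- In 4.1, separate removal by the investigator from refusal of all follow-up, so that removals for other reasons, such as noncompliance, still have a status.
- Leave the treatment-stopping criteria in 4.6 unchanged.

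The cost is a wording amendment to 4.1 and 4.6. No visits are added, because footnote 2 already asks for this follow-up. It is best done before subjects progress, since observation that has stopped may not be recoverable.
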